#### Randomization

Patients will be prospectively randomized after obtaining informed consent and confirmation of study eligibility. Patients will be randomized 3:1 via permuted block randomization, with blocks of varying sizes, stratified by cohort. The randomization sequence will be created by the Northwestern University Data Analysis and Coordinating Center (NUDACC), serving as the Data Coordinating Center (DCC) and uploaded to the REDCap database. Once a patient's eligibility has been confirmed, the research coordinator will access the randomization assignment via REDCap. The patient will be randomized and the assignment will be communicated to the pharmacy.

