3 INVESTIGATIONAL PLAN

3.1 Study Design

This will be a single-blind study where the patient will not know if they are receiving Auxora or Placebo. The first 4 patients will be enrolled in Cohort 1 and randomized 3:1 to Auxora or Placebo. If dose escalation occurs, the next 4 patients will be enrolled in Cohort 2 and randomized 3:1 to Auxora or Placebo. If dose escalation continues, the next 8 patients will be enrolled in Cohort 3 and randomized 3:1 to Auxora or Placebo. The decision to escalate dosing will be made by CalciMedica in consultation with the PI after the review of safety events in Cohorts 1 and 2.

Consultation between the PI and CalciMedica will occur if any patient receiving Auxora in Cohorts 1, 2 or 3 experiences one of the cardiac conduction events listed below during the 144 hours after the Start of the First Infusion of Study Drug (SFISD):

- QTcF interval of \geq 500 msec; or
- QTcF prolongation of \geq 60 msec as compared to baseline; or
- Mobitz Type II second degree atrioventricular (AV) block; or
- Third degree or high grade AV block; or
- Polymorphic Ventricular Tachycardia;

If one of the listed safety events occurs in a patient who is receiving Auxora in Cohort 1 but the event is not thought to be dose limiting, 4 additional patients will be enrolled in Cohort 1 and randomized 3:1 to Auxora versus Placebo for a total of 8 patients enrolled in the cohort, 6 randomized to Auxora and 2 to Placebo. The PI and CalciMedica will consult after all 8 patients are enrolled to determine if dose escalation to Cohort 2 will occur. If one of the listed safety events occurs in a patient who is receiving Auxora in Cohort 1 and the event is dose limiting, further dosing will not occur using the planned dose regimens but may occur using a regimen that provides lower total exposure of drug.

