6 PROCEDURES

6.1 Enrollment Procedures

Up to 32 patients will be enrolled in the study sequentially into three cohorts. If a patient discontinues study drug, withdraws consent, gets extubated or dies before the second BAL is performed, they will be replaced by the enrollment of an additional patient in the cohort.

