### **STUDY METHODS**

#### Trial Design

This will be a single center, prospective randomized trial of patients  $\geq$  18 years of age critical SARS-CoV-2 infection. The patient will not know if they are receiving Auxora or Placebo. The first 4 patients will be enrolled in Cohort 1 and randomized 3:1 to Auxora or Placebo. If dose escalation occurs, the next 8 patients will be enrolled in Cohort 2 and randomized 3:1 to Auxora or Placebo. If dose escalation continues, the next 8 patients will be enrolled in Cohort 3 and randomized 3:1 to Auxora or Placebo. The decision to escalate dosing will be made by CalciMedica in consultation with the PI after the review of safety events in Cohorts 1 and 2.

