#### Interim Analysis and Stopping Guidelines

As this is a dose-escalation study, Consultation between the PI and CalciMedica will occur if any patient receiving Auxora in Cohorts 1, 2 or 3 experiences one of the cardiac conduction events listed below during the 144 hours after the Start of the First Infusion of Study Drug (SFISD):

- QTcF interval of  $\geq$  500 msec; or
- QTcF prolongation of  $\geq$  60 msec as compared to baseline; or
- Mobitz Type II second degree atrioventricular (AV) block; or
- Third degree or high grade AV block; or
- Polymorphic Ventricular Tachycardia;

If one of the listed safety events occurs in a patient who is receiving Auxora in Cohort 1 but the event is not thought to be dose limiting, 4 additional patients will be enrolled in Cohort 1 and randomized 3:1 to Auxora versus Placebo for a total of 8 patients enrolled in the cohort, 6 randomized to Auxora and 2 to Placebo. The PI

and CalciMedica will consult after all 8 patients are enrolled to determine if dose escalation to Cohort 2 will occur. If one of the listed safety events occurs in a patient who is receiving Auxora in Cohort 1 and the event is dose limiting, further dosing will not occur using the planned dose regimens but may occur using a regimen that provides lower total exposure of drug.

If one of the listed safety events occurs in a patient who is receiving Auxora in Cohort 2 but the event is not thought to be dose limiting, 4 additional patients will be enrolled in Cohort 2 and randomized 3:1 to Auxora versus Placebo for a total of 12 patients enrolled in the cohort, 9 randomized to Auxora and 3 to Placebo. The PI and CalciMedica will consult after all 12 patients are enrolled to determine if dose escalation to Cohort 3 will occur. If one of the listed safety events occurs in a patient who is receiving Auxora in Cohort 2 and the event is dose limiting, further dosing will not occur in either Cohorts 2 or 3. 4 additional patients may be enrolled in Cohort 1 and randomized 3:1 to Auxora versus Placebo.

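### The SAP's blocks of varying sizes do not guarantee the stated 6:2 and 9:3 splits, or the implied 3:1, because nothing makes a block end where a cohort or expansion ends

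*SAP*

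**What the plan says.** The allocation rule is in the SAP, under Randomization: "Patients will be randomized 3:1 via permuted block randomization, with blocks of varying sizes, stratified by cohort". The coordinating center makes the sequence. No block sizes are given. Protocol section 8.3 only points to the study's randomization procedure.

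Cohorts are small and grow in steps of 4:
- Cohort 1 (Protocol 3.1; the SAP agrees): "The first 4 patients will be enrolled in Cohort 1 and randomized 3:1 to Auxora or Placebo".
- Cohort 2: the protocol has "the next 4 patients will be enrolled in Cohort 2 and randomized 3:1 to Auxora or Placebo", while the SAP has "the next 8 patients will be enrolled in Cohort 2 and randomized 3:1 to Auxora or Placebo".
- Cohort 3 (SAP, Trial Design; the protocol agrees): "the next 8 patients will be enrolled in Cohort 3 and randomized 3:1 to Auxora or Placebo".
- Each expansion adds 4 patients.

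For expanded cohorts the documents give counts, not just a ratio. Cohort 1 expands "for a total of 8 patients enrolled in the cohort, 6 randomized to Auxora and 2 to Placebo". In the SAP, Cohorts 2 and 3 expand "for a total of 12 patients enrolled in the cohort, 9 randomized to Auxora and 3 to Placebo". Protocol 3.1 gives the same counts for Cohorts 1 and 3. For an expanded Cohort 2, the protocol synopsis gives 6 and 2 of 8. For an unexpanded cohort of 4 only the ratio is stated; 3 and 1 is implied.

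Protocol 6.1 adds a replacement rule. For a patient lost before the second BAL for one of the listed reasons, "they will be replaced by the enrollment of an additional patient in the cohort".

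**The concern.** A permuted block holds an exact 3:1 ratio only if its size is a multiple of 4, and it delivers that ratio only when it is completed. Sizes that vary within a cohort imply at least one size of 8 or more. A cohort of 4 cannot complete such a block, and a cohort of 8 or 12 may close inside one. The split is then a random draw from a truncated block, although the documents print fixed counts.

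The numbers are small enough for one displaced assignment to matter. A cohort of 4 has one implied placebo patient. A 4:0 split leaves it with no concurrent placebo patient, and a 2:2 split leaves the safety review with 2 Auxora patients instead of 3.

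There is a related effect on expansions. Under Protocol 3.1, patients added to Cohort 1 or 2 after a dose-limiting event in the next cohort up receive a different regimen from the cohort's first patients. If Cohort 1 closed at 4:0 inside a block of 8, the remaining slots would be 6 − 4 = 2 Auxora and 2 placebo. The cohort total would read 6:2, yet neither regimen would have been allocated 3:1.

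**Working it through.** **Stated counts.** With N patients, 3N/4 receive Auxora and N/4 placebo: N = 8 gives 6 and 2; N = 12 gives 9 and 3. These match the documents. N = 4 gives 3 and 1.

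**Inputs.** The ratio, the blocking and the stratification come from SAP Randomization. Cohort sizes come from Protocol 3.1 and SAP Trial Design. Block sizes and their equal probabilities are assumptions, because the documents give none.

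**Truncated blocks.** If a cohort takes the first n patients of a block of size B with B/4 placebo slots, the placebo count is hypergeometric: P(x) = C(B/4, x) · C(3B/4, n − x) / C(B, n).

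- First 4 of a block of 8 (6 Auxora, 2 placebo; C(8,4) = 70): no placebo, C(6,4)/70 = 15/70 = 0.214; one placebo, 2 · C(6,3)/70 = 40/70 = 0.571; two placebo, C(6,2)/70 = 15/70 = 0.214.
- First 4 of a block of 12 (9 Auxora, 3 placebo; C(12,4) = 495): none, 126/495 = 0.255; one, 252/495 = 0.509; two, 108/495 = 0.218; three, 9/495 = 0.018.

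**Mixed sizes, cohort of 4.**

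- Sizes 4 and 8 equally likely: misses 3:1 in 0.5 × 30/70 = 0.214; no placebo in 0.5 × 15/70 = 0.107; 2 Auxora in 0.107.
- Sizes 4, 8 and 12 equally likely: misses in (0 + 0.429 + 0.491)/3 = 0.306; no placebo in (0 + 0.214 + 0.255)/3 = 0.156; 2 or fewer Auxora in (0 + 0.214 + 0.218 + 0.018)/3 = 0.150.

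**Larger cohorts.** These follow by conditioning on the first block. With sizes 4 and 8, a cohort of 8 is exact with probability 0.5 × 1 + 0.5 × 0.786 = 0.893, and one of 12 with probability 0.5 × 0.893 + 0.5 × 0.786 = 0.839.

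| Assumed sizes | Exact, n = 4 | Exact, n = 8 | Exact, n = 12 | No placebo, n = 4 | No placebo, n = 8 |
|---|---|---|---|---|---|
| 4, 8 | 78.6% | 89.3% | 83.9% | 10.7% | 0% |
| 4, 8, 12 | 69.4% | 73.4% | 80.9% | 15.6% | 0.6% |

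No placebo is impossible for n = 12 under either mix.

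**At least one opening cohort off its split.** SAP sizes 4, 8, 8: 1 − 0.786 × 0.893² = 37% with blocks of 4 and 8, and 1 − 0.694 × 0.734² = 63% with 4, 8 and 12. Protocol sizes 4, 4, 8: 45% and 65% by the same product. At least one opening cohort has no placebo patient in 11% to 17% (SAP sizes) or 20% to 29% (protocol sizes).

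**Aligned blocks.** With blocks of 4 throughout, or blocks of 4, 8 and 8 matched to the SAP's opening cohorts plus a new block of 4 for each expansion, every stated count is exact with probability 1.

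**Replacement.** Under blocks of 4, suppose one of the first 4 patients, chosen at random, is replaced from a new block. The four retained patients include no placebo with probability 0.25 × 0.75 = 0.19, one with 0.75 × 0.75 + 0.25 × 0.25 = 0.63, and two with 0.75 × 0.25 = 0.19.

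**The case against.** The SAP's wording also fits sizes that vary between cohorts (4, 8, 8), with a new block of 4 for each expansion. In that case every stated count is exact, and the coordinating center may have intended this. Every mixed-size percentage rests on assumed sizes and weights, and even then 69% to 89% of cohorts come out exact. This stands: the text fails to guarantee the splits. A reader might infer that it cannot deliver them, and the documents do not support that.

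Two other inferences go too far.
- **No control.** Protocol 10.6 and the SAP's pharmacodynamic analysis compare each dose arm with the placebo arm, which reads as one placebo group across cohorts. A 4:0 cohort would lack a concurrent placebo patient but would still have that comparator. The risk is also essentially confined to cohorts of 4.
- **Too few Auxora patients to escalate.** The documents set no minimum number for the escalation review. In a block of 8, a 4:0 split is as likely as 2:2. It can only be said that the review may rest on 2 exposed patients, not 3.

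Small blocks also have a cost. Only the patient is stated to be blinded, and the research coordinator sees assignments. In a known block of 4, on average (3 + 2 + 1 + 1)/4 = 1.75 of 4 assignments (44%) are certain beforehand, against about 2.29 of 8 (29%) in a known block of 8. This is a real trade-off. It is limited because exact cohort totals already make the last assignments of a cohort predictable.

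Finally, replacements break exactness under any scheme. This too stands, so the fix has to cover them.

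**Conclusion.** The point holds as a gap between a stated rule and stated counts. As written, the SAP does not guarantee 6:2, 9:3 or the implied 3:1, because it allows a block to straddle a cohort or expansion boundary. The combinatorial result for a block of 8 cut at 4 (0.21, 0.57, 0.21) needs no assumption beyond that cut. The 21% and 31% chances of missing 3:1 in a cohort of 4, and the 11% and 16% chances of no placebo patient, assume equally likely sizes of 4 and 8, or of 4, 8 and 12, varying within a cohort. If the actual list already aligns blocks with boundaries, the risk before replacement is zero and the SAP only needs to say so.

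**What to change.** First reconcile the opening size of Cohort 2 (4 in Protocol 3.1, 8 in SAP Trial Design), since the block plan depends on it. Then, in SAP Randomization, require blocks to end at every cohort and expansion boundary:

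- a cohort opening with 4: one block of 4;
- a cohort opening with 8: either 4 + 4 or a single 8, chosen at random and concealed, which keeps some variation in size;
- each expansion of 4: its own new block of 4.

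State how replacements under Protocol 6.1 are allocated, and that the exact counts apply before replacement. If the coordinating center prefers to keep unaligned blocks, describe 6:2 and 9:3 as expected counts in both documents.

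The cost is one SAP paragraph and a regenerated list. The downside is that later assignments within small blocks become more predictable to staff, who are not stated to be blinded. The SAP should acknowledge this and keep the block sizes and the sequence concealed from the site.

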#### Interim Analysis and Stopping Guidelines

As this is a dose-escalation study, Consultation between the PI and CalciMedica will occur if any patient receiving Auxora in Cohorts 1, 2 or 3 experiences one of the cardiac conduction events listed below during the 144 hours after the Start of the First Infusion of Study Drug (SFISD):

- QTcF interval of  $\geq$  500 msec; or
- QTcF prolongation of  $\geq$  60 msec as compared to baseline; or
- Mobitz Type II second degree atrioventricular (AV) block; or
- Third degree or high grade AV block; or
- Polymorphic Ventricular Tachycardia;

If one of the listed safety events occurs in a patient who is receiving Auxora in Cohort 1 but the event is not thought to be dose limiting, 4 additional patients will be enrolled in Cohort 1 and randomized 3:1 to Auxora versus Placebo for a total of 8 patients enrolled in the cohort, 6 randomized to Auxora and 2 to Placebo. The PI

and CalciMedica will consult after all 8 patients are enrolled to determine if dose escalation to Cohort 2 will occur. If one of the listed safety events occurs in a patient who is receiving Auxora in Cohort 1 and the event is dose limiting, further dosing will not occur using the planned dose regimens but may occur using a regimen that provides lower total exposure of drug.

If one of the listed safety events occurs in a patient who is receiving Auxora in Cohort 2 but the event is not thought to be dose limiting, 4 additional patients will be enrolled in Cohort 2 and randomized 3:1 to Auxora versus Placebo for a total of 12 patients enrolled in the cohort, 9 randomized to Auxora and 3 to Placebo. The PI and CalciMedica will consult after all 12 patients are enrolled to determine if dose escalation to Cohort 3 will occur. If one of the listed safety events occurs in a patient who is receiving Auxora in Cohort 2 and the event is dose limiting, further dosing will not occur in either Cohorts 2 or 3. 4 additional patients may be enrolled in Cohort 1 and randomized 3:1 to Auxora versus Placebo.

If one of the listed safety events occurs in a patient who is receiving Auxora in Cohort 3 but the event is not felt to be dose limiting, 4 additional patients will be enrolled in Cohort 3 and randomized 3:1 to Auxora versus Placebo for a total of 12 patients enrolled in the cohort, 9 randomized to Auxora and 3 to Placebo. If one of the listed safety events occurs in a patient who is receiving Auxora in Cohort 3 and the event is dose limiting, further dosing will not occur in Cohort 3. 4 additional patients may be enrolled in Cohort 2 and randomized 3:1 to Auxora versus Placebo.

There will be no formal interim analyses for efficacy. In addition to the protocol specified safety events specified above, Adverse Events (AEs) and Serious Adverse Events (SAEs) will be recorded on dedicated CRFs and will be reviewed on an ongoing basis by the DSMB.

The sponsor, CalciMedica, reserves the right to terminate the study at any time or for any reason including:

- A directive from the FDA
- A lack of enrollment
- A recommendation from the IDMC

## **STATISTICAL PRINCIPLES**

### Level of significance

All analyses will assume a two-sided type I error rate of 0.05.

### Analysis population

Pharmacodynamic and Efficacy analyses will be based on an Intention-to-treat (ITT) principle. All data will be included and no subjects will be excluded because of protocol violations. Safety analyses will be based on a per-protocol principle, whereby subjects will be included in the treatment group according to the treatment they actually receive.

### Power Considerations

Sample size considerations were based on precision estimates and the ability to construct 95% confidence intervals around point estimates for pharmacodynamics endpoints with reasonable precision. Sample sizes as small as 9 patients per arm will allow for construction of 95% confidence intervals with half-widths as small as 0.77 standard deviation units.

For other assessments, the study is not powered for analysis with inferential statistics.

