	
• Third degree or high grade AV block; or• Polymorphic Ventricular Tachycardia; 
If one of the listed safety events occurs in a patient who is receiving Auxora in Cohort 1 but the event is not thought to be dose limiting, 4 additional patients will be enrolled in Cohort 1 and randomized 3:1 to Auxora versus Placebo for a total of 8 patients enrolled in the cohort, 6 randomized to Auxora and 2 to Placebo. The PI and CalciMedica will consult after all 8 patients are enrolled to determine if dose escalation to Cohort 2 will occur. If one of the listed safety events occurs in a patient who is receiving Auxora in Cohort 1 and the event is dose limiting, further dosing will not occur using the planned dose regimens but may occur using a regimen that provides lower total exposure of drug.
 
If one of the listed safety events occurs in a patient who is receiving Auxora in Cohort 2 but the event is not thought to be dose limiting, 4 additional patients will be enrolled in Cohort 2 and randomized 3:1 to Auxora versus Placebo for a total of 8 patients enrolled in the cohort, 6 randomized to Auxora and 2 to Placebo. The PI and CalciMedica will consult after all 8 patients are enrolled to determine if dose escalation to Cohort 3 will occur. If one of the listed safety events occurs in a patient who is receiving Auxora in Cohort 2 and the event is dose limiting, further dosing will not occur in either Cohorts 2 or 3. 4 additional patients may be enrolled in Cohort 1 and randomized 3:1 to Auxora versus Placebo. The 4 additional patients in Cohort 1 will receive a dose regimen of an initial infusion followed by continuous infusion for 48 hours.
 
If one of the listed safety events occurs in a patient who is receiving Auxora in Cohort 3 but the event is not felt to be dose limiting, 4 additional patients will be enrolled in Cohort 3 and randomized 3:1 to Auxora versus Placebo for a total of 12 patients enrolled in the cohort, 9 randomized to Auxora and 3 to Placebo. If one of the listed safety events occurs in a patient who is receiving Auxora in Cohort 3 and the event is dose limiting, further dosing will not occur in Cohort 3. 4 additional patients may be enrolled in Cohort 2 and randomized 3:1 to Auxora versus Placebo. The 4 additional patients in Cohort 2 will receive a dose regimen of an initial infusion followed by continuous infusion for 72 hours.
 
A study physician or appropriately trained delegate will perform assessments at Screening, immediately prior to the SFISD, and then every 24 hours (± 1 hours) until 240 hours after the SFISD. After 240 hours from the SFISD, the patient will be assessed q48 hours until Day 30 after the SFISD, or until discharge if earlier. Patients who are discharged before Day 25 after the SFISD will be followed-up at Day 30 (± 5 days). Patients will be followed up at Day 60 (± 5 days). for a safety and mortality assessment.

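### The stated precision (9 patients per arm, half-width 0.77 SD) fits no dose arm and no placebo arm of the unexpanded design in either document

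*SAP*

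**What the plan says.** The SAP (Power Considerations) says: "Sample sizes as small as 9 patients per arm will allow for construction of 95% confidence intervals with half-widths as small as 0.77" SD units. The same sentence stands in the Protocol synopsis and in Protocol 10.1. It is the only basis given for the sample size; there is no effect size, assumed SD or power.

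The cohort sizes are set elsewhere. Both documents start with 4 patients in Cohort 1 and plan 8 in Cohort 3. For Cohort 2, Protocol 3.1 says "the next 4 patients will be enrolled in Cohort 2 and randomized 3:1 to Auxora or Placebo", while the SAP (Trial Design) says "the next 8 patients will be enrolled in Cohort 2 and randomized 3:1 to Auxora or Placebo".

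The documents also differ on Cohort 2 after a safety addition. The Protocol synopsis says "The PI and CalciMedica will consult after all 8 patients are enrolled to determine if dose escalation to Cohort 3 will occur"; the SAP (Interim Analysis and Stopping Guidelines) says "The PI and CalciMedica will consult after all 12 patients are enrolled to determine if dose escalation to Cohort 3 will occur".

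On allocation, the SAP says "Patients will be randomized 3:1 via permuted block randomization, with blocks of varying sizes, stratified by cohort". Protocol 6.1 caps enrolment: "Up to 32 patients will be enrolled in the study sequentially into three cohorts". The SAP gives no cap.

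The primary pharmacodynamic analysis (Protocol 10.6; SAP, Pharmacodynamic Analysis) summarises change with 95% confidence intervals separately for each dose arm. It then allows comparisons of each dose arm with placebo.

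**The concern.** The sentence presents 9 per arm as a lower bound, yet no base cohort has more than 8 patients in total, placebo included. A precision statement can justify a sample size only if it describes the arms that will be analysed.

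Protocol 1.7 gives the purpose of the study as finding the optimal dose from markers in BAL fluid. A reader would take from the sentence that each dose arm's mean change will be known to within about three quarters of an SD. A three-patient arm is far less precise than that.

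Two related points bear on any correction:

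- Planned precision cannot be stated in one set of figures while the documents disagree on Cohort 2.
- Protocol 10.1 lists BAL flow cytometry and single-cell RNA sequencing among the other assessments, apart from the pharmacodynamic endpoints that the precision sentence covers. Protocol 10.2 places BAL cell proportions and single-cell RNA sequencing under the primary pharmacodynamic endpoint.

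**Working it through.** **Inputs**

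- Stated n and half-width: 9 per arm, 0.77 SD (SAP, Power Considerations; Protocol synopsis and 10.1).
- Interval: two-sided 95% (same sentence; SAP, Level of significance).
- Base cohorts: 4/4/8 (Protocol 3.1) and 4/8/8 (SAP, Trial Design), allocated 3:1.
- Cap: 32 patients (Protocol 6.1).

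The counts below assume exact 3:1 in each cohort and leave out replacements under Protocol 6.1.

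**1. The plan's own figure.** For one arm's mean with its own SD, half-width/SD = t(0.975, n−1)/√n. At n=9 this is 2.306/3 = 0.769, which rounds to 0.77. No other n from 2 to 39 rounds to 0.77. A normal quantile gives 0.653, and a difference between two arms of nine gives 0.999. So 0.77 is correct for one arm's mean at n=9.

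**2. Planned arm sizes**

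| Plan | Cohorts | Auxora by cohort | Placebo by cohort | Pooled placebo | Total |
|---|---|---|---|---|---|
| Protocol | 4/4/8 | 3/3/6 | 1/1/2 | 4 | 16 |
| SAP | 4/8/8 | 3/6/6 | 1/2/2 | 5 | 20 |

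Whatever the block sizes, a cohort of 8 cannot supply 9 patients to one arm.

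**3. Half-widths on the same basis (own SD, n−1 df)**

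| n | Half-width (SD) | Ratio to 0.769 |
|---|---|---|
| 3 | 2.484 | 3.23 |
| 4 | 1.591 | 2.07 |
| 5 | 1.242 | 1.62 |
| 6 | 1.049 | 1.37 |
| 9 | 0.769 | 1.00 |

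If placebo is not pooled, Cohorts 1 and 2 (Protocol) or Cohort 1 (SAP) have one placebo patient each, and no own-SD interval exists for them.

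**4. A more favourable basis: common SD over four arms.** Half-width/SD = t(0.975, N−4)/√n.

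- Protocol, N=16, 12 df: 1.258 (n=3), 0.889 (n=6), 1.089 (placebo, n=4).
- SAP, N=20, 16 df: 1.224 (n=3), 0.865 (n=6), 0.948 (placebo, n=5).

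The ratios to 0.769 run from 1.13 to 1.64. Every arm is still wider than stated.

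**5. With expansion**

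- One addition of 4 in every cohort, Protocol: 8+8+12 = 28 patients, Auxora 6/6/9 and placebo 7. Own-SD half-widths are 1.05/1.05/0.77 and 0.92.
- The same in the SAP: 8+12+12 = 32 patients, Auxora 6/9/9 and placebo 8. Half-widths are 1.05/0.77/0.77 and 0.84.
- Nine in all three dose arms and in pooled placebo: 3×9 = 27 Auxora and 27/3 = 9 placebo, 36 in total, against a cap of 32. At 32 patients, placebo is 32/4 = 8.

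**The case against.** **Expansion is part of the written design.** The Protocol's headline number is the maximum of 32, and both documents give 9 Auxora patients for an enlarged Cohort 3. The SAP gives 9 for an enlarged Cohort 2 as well. Other paths lead there too. After a dose-limiting event in Cohort 3, "4 additional patients may be enrolled in Cohort 2 and randomized 3:1 to Auxora versus Placebo" (SAP; the Protocol has the same provision). Cohort 2 could then reach 4+4+4 = 12 patients with 9 on Auxora (Protocol), or 8+4+4 = 16 with 12 on Auxora (SAP, half-width 0.64 SD). This gives a visible possible source for the 9. Every such path depends on a safety event, though, and in the Protocol the last four patients would receive a different infusion regimen. With one addition per cohort, Cohort 1 stays at 6 Auxora patients; pooled placebo stays below 9 even at the cap.

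**Replacements can push a cohort past its planned size.** Protocol 6.1 replaces patients who miss the second BAL, and the intention-to-treat set keeps the replaced patients. This stands as a qualification: a safety addition is not strictly the only way to randomise 9 to an arm. Replacement mainly preserves the evaluable number and is not meant to raise it.

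**Arm could mean all Auxora doses pooled.** Protocol 8.13.6 and 8.13.7 do compare Auxora with placebo. Pooled Auxora would be 12 (2.201/√12 = 0.64 SD) or 15 (2.145/√15 = 0.55 SD), both within 0.77. But the stated primary summary is by dose arm, and placebo would still be 4 or 5.

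**The sentence is conditional and the study descriptive.** It says what 9 patients would allow, and no decision rule uses 0.77. That limits the consequence. It does not make the sentence a justification of the sizes planned.

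**Conclusion.** The concern holds. The figure 0.77 contains no arithmetic error; the inconsistency is between the stated sample size and the design. No dose arm and no placebo arm has 9 patients in the unexpanded plan of either document. Planned half-widths are 1.4 to 3.2 times the stated value on the basis that produces it, and 1.1 to 1.6 times with a common SD.

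The conclusion is the same under either Cohort 2 size. It rests on exact 3:1 allocation, on placebo pooled over cohorts (the documents refer to a placebo arm without saying so), and on leaving replacements aside. The 36-patient figure also assumes that all three cohorts open. Whether replacements count toward the 32 is not stated.

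This should be fixed, because the sentence is the sole basis for the sample size. The computed results are not affected.

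**What to change.** 1. Reconcile the Cohort 2 size between Protocol and SAP: base 4 or 8, expanded 8 or 12. I take no position on which is right.
2. Replace the precision sentence in the synopsis, Protocol 10.1 and the SAP with half-widths at the agreed arm sizes. On the own-SD basis these are 2.48 SD (n=3) and 1.05 SD (n=6) for dose arms, and 1.59 SD (n=4) or 1.24 SD (n=5) for pooled placebo. If a common SD is intended, use the figures in step 4 of the working.
3. State the SD and degrees-of-freedom basis, whether placebo is pooled over cohorts, and whether added patients on a different infusion regimen (Protocol 3.1) count in that cohort's dose arm.
4. Say that 0.77 SD applies only to an arm that reaches 9 through expansion.
5. In Protocol 10.1, keep the statement that the study is not powered for inference. Reword the list of other assessments so that it does not separate the primary BAL flow cytometry endpoint from the endpoints the precision statement covers.

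The cost is wording in three places and one decision on Cohort 2. No patients are added. The only downside is a less favourable stated precision.
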